## 10.9 Appendix 9: Standard Toxicity Grading for Laboratory Tests According to National Cancer Institute Common Terminology Criteria for Adverse Events (NCI-CTCAE) v4.0

**Table 24. Standard Toxicity Grading for Laboratory Tests According to National Cancer Institute Common Terminology Criteria for Adverse Events (NCI-CTCAE) v4.0**

Test Name	Test Code	Units 	Direction of Change / AE Term	CTCAE Grade 					NCI Ref.		
				0	1	2	3	4	Version	Page	Units
Alanine Aminotransferase (ALT/SGPT)	ALT	n/a	Increase/ Alanine aminotransferase increased	WNL	>ULN - ≤ 3.0×ULN	>3.0×ULN - ≤ 5.0×ULN	>5.0×ULN - ≤ 20.0×ULN	>20.0×ULN	4.0	107	n/a
Albumin	ALB	g/dL	Decrease/ Hypoalbuminemia	WNL	≥3 - <LLN	≥2 - <3	<2		4.0	116	g/dL
Alkaline Phosphatase	ALP	n/a	Increase/ Alkaline phosphatase increased	WNL	>ULN - ≤ 2.5×ULN	>2.5×ULN - ≤ 5.0×ULN	>5.0×ULN - ≤ 20.0×ULN	>20.0×ULN	4.0	107	n/a
Amylase	AMY	n/a	Increase/ Serum amylase increased	WNL	>ULN - ≤ 1.5×ULN	>1.5×ULN - ≤ 2.0×ULN	>2.0×ULN - ≤ 5.0×ULN	>5.0×ULN	4.0	112	n/a
Aspartate Aminotransferase (AST/SGOT)	AST	n/a	Increase/ Aspartate aminotransferase increased	WNL	>ULN - ≤ 3.0×ULN	>3.0×ULN - ≤ 5.0×ULN	>5.0×ULN - ≤ 20.0×ULN	>20.0×ULN	4.0	107	n/a
Calcium Corrected 	CACOR	mg/dL	Increase/ Hypercalcemia	WNL	>ULN - ≤ 11.5	>11.5 - ≤ 12.5	>12.5 - ≤ 13.5	>13.5	4.0	115	mg/dL
Calcium Corrected 	CACOR	mg/dL	Decrease/ Hypocalcemia	WNL	≥8.0 - <LLN	≥7.0 - <8.0	≥6.0 - <7.0	<6.0	4.0	116	mg/dL
Total Cholesterol	TCHOL	mg/dL	Increase/ Cholesterol high	WNL	>ULN - ≤ 300	>300 - ≤ 400	>400 - ≤ 500	>500	4.0	109	mg/dL
Creatine Phosphokinase	CPK	n/a	Increase/ CPK increased	WNL	>ULN - ≤ 2.5×ULN	>2.5×ULN - ≤ 5×ULN	>5×ULN - ≤ 10×ULN	>10×ULN	4.0	109	n/a
Creatinine	CREAT	n/a	Increase/ Creatinine increased	WNL	>ULN - ≤ 1.5×ULN or >ULN - ≤ 1.5×baseline	>1.5×ULN - ≤ 3.0×ULN or >1.5×ULN - ≤ 3.0×baseline	>3.0×ULN - ≤ 6.0×ULN or >3.0×ULN - ≤ 3.0×baseline	>6.0×ULN	4.0	109	n/a
Estimated glomerular filtration rate	GFR	mL/min per 1.73 m 	Decrease/ Chronic kidney disease	Not applicable 	Not applicable 	30 - 59	15 - 29	<15	4.0	147	mL/min per 1.73 m 

Gamma Glutamyl Transferase (GGT)	GGT	n/a	Increase/ GGT increased	WNL	>ULN - ≤2.5×ULN	>2.5×ULN - ≤5.0×ULN	>5.0×ULN - ≤20.0×ULN	>20.0×ULN	4.0	110	n/a
Glucose	GLUC	mg/dL	Decrease/ Hypoglycemia	WNL	≥55 - <LLN	≥40 - <55	≥30- <40	<30	4.0	117	mg/dL
Hemoglobin	HGB	g/dL	Increase/ Hemoglobin increased	WNL	Increase in >0 - 2 g/dL above ULN or above baseline if baseline is above ULN	Increase in >2 - 4 g/dL above ULN or above baseline if baseline is above ULN	Increase in >4 g/dL above ULN or above baseline if baseline is above ULN		4.0	111	g/dL
Hemoglobin	HGB	g/dL	Decrease/ Anemia	WNL	≥10 - <LLN	≥8 - <10.0	<8		4.0	3	g/dL
Leukocytes (WBC)	WBC	10  /μL	Decrease/ White blood cell decreased	WNL	≥3.0 - <LLN	≥2.0 - <3.0	≥1.0 - <2.0	<1.0	4.0	113	10  /μL
Lymphocytes, Absolute Units	LYMP HAB	10  /μL	Decrease/ Lymphocyte count decreased	Not applicable	Not applicable	≥0.5 - <0.8	≥0.2 - <0.5	<0.2	4.0	111	10  /μL
Lymphocytes, Absolute Units	LYMP HAB	10  /μL	Increase/ Lymphocyte count increased	Not applicable		>4 - 20	>20		4.0	111	10  /μL
Magnesium	MG	mg/dL	Increase/ Hypermagnesemia	WNL	>ULN - ≤3.0		>3.0 - ≤8.0	>8.0	4.0	115	mg/dL
Magnesium	MG	mg/dL	Decrease/ Hypomagnesemia	WNL	≥1.2 - <LLN	≥0.9 - <1.2	≥0.7 - <0.9	<0.7	4.0	117	mg/dL
Absolute Neutrophil Count	ANC	10  /μL	Decrease/ Neutrophil count decreased	Not applicable	Not applicable	≥1.0 - <1.5	≥0.5 - <1.0	<0.5	4.0	112	10  /μL
Phosphate (Phosphorus)	PHOS	mg/dL	Decrease/ Hypophosphatemia	WNL	Not applicable	≥2.0 - <2.5	≥1.0 - <2.0	<1.0	4.0	117	mg/dL
Platelets	PLT	10  /μL	Decrease/ Platelet count decreased	WNL	≥75.0 - <LLN	≥50.0 - <75.0	≥25.0 - <50.0	<25.0	4.0	112	10  /μL
Potassium	K	mEq/L	Increase/ Hyperkalemia	WNL	>ULN - ≤5.5	>5.5 - ≤6.0	>6.0 - ≤7.0	>7.0	4.0	115	mEq/L 
Potassium 	K	mEq/L	Decrease/ Hypokalemia	WNL		≥3.0 - <LLN	≥2.5 - <3.0	<2.5	4.0	117	mEq/L 
Urine Protein 	UPROT		Increase/ Proteinuria	WNL	+	++	+++ or ++++		4.0	149	n/a
Sodium	NA	mEq/L	Increase/ Hyponatremia	WNL	>ULN - ≤150	>150 - ≤155	>155 - ≤160	>160	4.0	116	mEq/L 

Sodium	NA	mEQ/L	Decrease/ Hyponatremia	WNL	$\geq 130$ - <LLN		$\geq 120$ - <130	<120	4.0	117	mEQ/L 
Total Bilirubin	TBI LI	n/a	Increase/ Blood bilirubin increased	WNL	>ULN - $\leq 1.5 \times$ ULN	>1.5×U LN - $\leq 3.0 \times$ U LN	>3.0×U LN - $\leq 10.0 \times$ ULN	>10.0 ×ULN	4.0	107	n/a
Triglycerides	TRIG	mg/dL	Increase/ Hypertriglyceridemia	WNL	>ULN  - $\leq 300$	>300 - $\leq 500$	>500 - $\leq 1000$	>1000	4.0	116	mg/dL
Uric Acid 	UACID	mg/dL	Increase/ Hyperuricemia	WNL			>ULN - 10	>10	4.0	116	mg/dL

 "n/a" is specified if the criteria are based strictly on a comparison of the value to its reference range.

 WNL = Within Normal Limits; LLN = Lower Limit of Normal; ULN = Upper Limit of Normal.

 **Calcium Corrected** will be derived using the following formula: Calcium Corrected =  $0.8 \times (4.0 - \text{Albumin}) + \text{Calcium}$ , where 4.0 represents the average albumin level in g/dL, Albumin is measured in unit of g/dL, and Calcium is measured in unit of mg/dL.

 Hypokalemia Grade 2 is the same as Grade1 but has additional clinical criteria that cannot be assessed. Therefore, it was decided to grade all criteria falling within  $\geq 3.0$  - <LLN as grade 2.

 For Urine Protein, the maximum category is "++++", while NCI CTCAE version4.0 doesn't define "+++", "++++". So, these are defined as grade 3 per internal discussion.

 Hyperuricemia Grade 3 is the same as Grade1 but has additional clinical criteria that cannot be assessed. Therefore, it was decided to grade all criteria falling within >ULN – 10 mg/dL as grade 3.

 For hyperkalemia, hypokalemia, hypernatremia and hyponatremia, the unit in the NCI reference is mmol/L, which has been converted to mEq/L by multiplying 1.

 For ANC, LYMPHAB, GFR, there are no reference range in central laboratory, so, NCI CTCAE grading scale is only defined for not-related reference range category. For PHOS, LLN=2.5mg/dL, while NCI Grade 1 is defined " $\geq 2.5$  - <LLN", so Grade 1 can't be defined.

 For TRIG, the upper limit of normal range is 149 mg/dL. Therefore, WNL for Grade 0 is up to 149 mg/dL. But the lower limit of Grade 1 is originally more than 150 mg/dL. So, the definition for the lower limit of grade 1 is changed from 150 mg/dL to ULN.

- Hyperuricemia (see pg. 116 of NCI document) cannot be assessed accurately without knowing whether or not the subject was experiencing physiologic consequences, so it is not included in the table.
- Hemoglobinuria (see pg. 148 of NCI document) cannot be assessed accurately without knowing clinical or diagnostic observations, so it is not included in the table.
- Troponin T (see pg. 109 of NCI document) cannot be assessed accurately without knowing manufacturer ranges, so it is not included in the table.

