3.4.1.1 Criteria for Suspension or Interruption of the Study Drug

The investigator/sub-investigator will immediately suspend or interrupt the study drug if any of the following becomes applicable during the treatment period:

1. Clinical laboratory tests yielded any of the following results:
 - Hemoglobin < 8.0 g/dL
 - Absolute neutrophil count < 500/ μ L
 - Absolute lymphocyte count < 500/ μ L
 - Platelet count < 50000/ μ L
 - Creatinine (serum) levels measured at 2 consecutive hospital visits: above 150% of the baseline level
 - CPK > 10 \times ULN
2. β -D-glucan test result of 11 pg/mL or higher.
3. The subject requires a medication whose concomitant administration is prohibited in the protocol because of possible drug–drug interaction.
4. The subject is suspected to be pregnant.
5. The investigator/sub-investigator judged it appropriate in the interest of the subject to suspend or interrupt the study drug.
6. The sponsor made a request to suspend or interrupt the study drug out of safety concerns for the subject.

- CONFIDENTIAL -

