### **Laboratory Tests for NCI-CTC Toxicity Grading**

Laboratory test results for the select laboratory tests will be graded programmatically using the standardized NCI-CTC toxicity grading criteria (Grade 0, 1, 2, 3, 4) specified in the 10.8 Appendix8 for this study. Shift-from-baseline to worst value up to Week 12 or during entire period will be provided.

Note: AEs in this study are graded the investigator using NCI-CTAE Grade (1, 2, 3, 4, 5).

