**Table 3. Select Laboratory Variables and Corresponding Reference Ranges**

Select Laboratory Variable	Reference Range	Highest/Lowest
Aspartate Aminotransferase (AST)	$\geq 1 \times \text{ULN}$ to $< 2 \times \text{ULN}$ $\geq 2 \times \text{ULN}$ to $< 3 \times \text{ULN}$ $\geq 3 \times \text{ULN}$	Highest
Alanine Aminotransferase (ALT)	$\geq 1 \times \text{ULN}$ to $< 2 \times \text{ULN}$ $\geq 2 \times \text{ULN}$ to $< 3 \times \text{ULN}$ $\geq 3 \times \text{ULN}$	Highest
Alkaline Phosphatase (ALP)	$> 2 \times \text{ULN}$ to $\leq 3 \times \text{ULN}$ $> 3 \times \text{ULN}$ to $\leq 5 \times \text{ULN}$ $> 5 \times \text{ULN}$	Highest
Total Bilirubin	$> 1.5 \times \text{ULN}$	Highest
Total Bilirubin	$\geq 1 \times \text{ULN}$ to $< 2 \times \text{ULN}$ $\geq 2 \times \text{ULN}$ to $< 3 \times \text{ULN}$ $\geq 3 \times \text{ULN}$	Highest
Low-Density Lipoprotein (LDL)	$> 160 \text{ mg/dL}$	Highest
Low-Density Lipoprotein (LDL)	$< 100 \text{ mg/dL}$ 100 to $< 130 \text{ mg/dL}$ 130 to $< 160 \text{ mg/dL}$ 160 to $< 190 \text{ mg/dL}$ $\geq 190 \text{ mg/dL}$	Highest
Hemoglobin (HGB)	$\geq 8.0$ to $< 10.0 \text{ g/dL}$ $< 8.0 \text{ g/dL}$	Lowest
Hemoglobin (HGB)	$\geq (\text{Baseline-2})$ to $< (\text{Baseline-1}) \text{ g/dL}$ $< (\text{Baseline-2}) \text{ g/dL}$	Lowest
Hemoglobin (HGB)	
 
Mild to Moderate: decrease from baseline <math>\geq 1</math> to <math>\leq 2 \text{ g/dL}</math>,
 
Severe: decrease from baseline <math>> 2</math> to <math>< 3 \text{ g/dL}</math> or absolute value <math>> 7</math> and <math>< 8 \text{ g/dL}</math>,
 
Potentially Life Threatening: decrease from baseline <math>\geq 3</math> or absolute value <math>\leq 7 \text{ g/dL}</math>
 
	Lowest
Creatine Phosphokinase (CPK)	$> 500$ to $\leq 2,000 \text{ U/L}$ $> 2,000 \text{ U/L}$	Highest
Creatine Phosphokinase (CPK)	$> 5 \times \text{Baseline}$	Highest
Creatine Phosphokinase (CPK)	$> 2 \times \text{ULN}$ to $\leq 5 \times \text{ULN}$ $> 5 \times \text{ULN}$ to $\leq 10 \times \text{ULN}$ $> 10 \times \text{ULN}$	Highest

Select Laboratory Variable	Reference Range	Highest/Lowest
Creatinine	> 1.5 × Baseline to ≤ 3.0 × Baseline > 3.0 × Baseline	Highest
Absolute Neutrophil Count (ANC)	≥ 1,500 to < 2,000 / mm  ≥ 500 to < 1,500 / mm  < 500 / mm 	Lowest
Lymphocytes	≥ 200 to < 500 /uL < 200 /uL	Lowest

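### SAP Table 24 gives the creatinine baseline criteria a ULN lower bound and a baseline upper bound, so they do nothing when baseline is normal and make grades overlap when it is raised

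*SAP*

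**What the plan says.** Table 24 offers two alternative limbs for each of creatinine Grades 1 to 3:

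- Grade 1: ">ULN - ≤ 1.5×ULN or >ULN - ≤ 1.5×baseline"
- Grade 2: ">1.5×ULN - ≤ 3.0×ULN or >1.5×ULN - ≤ 3.0×baseline"
- Grade 3: ">3.0×ULN - ≤ 6.0×ULN or >3.0×ULN - ≤ 3.0×baseline", of which the baseline limb is ">3.0×ULN - ≤ 3.0×baseline"

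Grade 0 is within normal limits. Grade 4 is above 6.0 × ULN, with no baseline limb.

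Section 7.5.2 has a program assign the grades and summarises them as follows: "Shift-from-baseline to worst value up to Week 12 or during entire period will be provided".

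The documents use baseline multiples for creatinine in two other places. Table 3 of SAP Section 7.5.2 counts subjects by highest value in the bands "> 1.5 × Baseline to ≤ 3.0 × Baseline > 3.0 × Baseline". Protocol Section 3.4.1.1 lists among its suspension criteria "Creatinine (serum) levels measured at 2 consecutive hospital visits: above 150% of the baseline level", with no ULN condition.

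**The concern.** A baseline limb is there to register a rise relative to the subject's own starting value. These limbs start at a ULN multiple, so a value must already have crossed the ULN threshold for that grade before baseline is considered.

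This does not look like a documented adaptation. Footnotes 4, 5, 6, 8 and 9 of Table 24 explain changes to other rows, and none covers creatinine. The row for increased hemoglobin says when its baseline condition applies; the creatinine row does not. The pattern repeats in all three grades, so an extraction error is unlikely.

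At stake is one safety display for a parameter of interest. Protocol Section 1.3 reports raised creatinine and lowered eGFR against placebo in the Japanese phase II study. A graded creatinine shift table should be programmable in only one way, and a reader should be able to tell whether it reflects relative rises.

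**Working it through.** The plan states no figure to reproduce; this is a check of the inequalities. ULN is not given, so everything is in ULN units: b = baseline/ULN and x = value/ULN.

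**Printed rule (Table 24)**

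- Grade 1: 1 < x ≤ 1.5, or 1 < x ≤ 1.5b
- Grade 2: 1.5 < x ≤ 3, or 1.5 < x ≤ 3b
- Grade 3: 3 < x ≤ 6, or 3 < x ≤ 3b
- Grade 4: x > 6

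**Baseline at or below ULN (b ≤ 1).** Here 1.5b ≤ 1.5 and 3b ≤ 3. The Grade 1 and Grade 2 baseline limbs therefore sit inside their ULN limbs, and the Grade 3 limb is empty. On a 0.01 grid (b from 0.30 to 1.00, x from 0.05 to 7.99; 71 × 795 = 56,445 cells), the printed rule differed from a ULN-only rule in 0 cells.

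**Any baseline.** The Grade 2 and Grade 3 baseline limbs both end at 3b, and the Grade 3 limb starts higher. It is always contained in the Grade 2 limb.

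**Baseline above ULN (b > 1).** The grades overlap:

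- b = 1.2: 1.5b = 1.8 and 3b = 3.6. Values above 1.5 up to 1.8 × ULN meet Grades 1 and 2; values above 3.0 up to 3.6 × ULN meet Grades 2 and 3.
- b = 1.6, value unchanged: x = 1.6 exceeds 1.5 and is at most 1.5b = 2.4, so it meets Grades 1 and 2. The subject has no unique grade even at baseline.
- b = 2.5: 3b = 7.5. Values above 6.0 up to 7.5 × ULN meet Grades 2, 3 and 4.

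The worst-value instruction in Section 7.5.2 chooses between values, not between grades for one value. Nor would a highest-grade rule alone rescue the limbs: every value in a baseline limb that lies beyond its own ULN limb already meets a higher grade on ULN, so the row would again be ULN-only.

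**Comparison with the SAP's own baseline bands.** The last column takes the higher of the ULN grade and a baseline grade, with above 1.5 to 3.0 × baseline as Grade 2 and above 3.0 × baseline as Grade 3. That mapping is an assumption, taken from the 1.5 and 3.0 multiples in Table 24.

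| Baseline (× ULN) | Fold rise | Value (× ULN) | Printed grade | Table 3 band (× baseline) | Grade with baseline multiples |
|---|---|---|---|---|---|
| 0.35 | 2.5 | 0.875 | 0 | >1.5 to ≤3.0 | 2 |
| 0.35 | 4 | 1.40 | 1 | >3.0 | 3 |
| 0.5 | 2 | 1.00 | 0 | >1.5 to ≤3.0 | 2 |
| 0.5 | 2.9 | 1.45 | 1 | >1.5 to ≤3.0 | 2 |
| 0.5 | 5 | 2.50 | 2 | >3.0 | 3 |
| 0.7 | 2 | 1.40 | 1 | >1.5 to ≤3.0 | 2 |
| 0.7 | 4 | 2.80 | 2 | >3.0 | 3 |
| 0.9 | 3.1 | 2.79 | 2 | >3.0 | 3 |
| 1.0 | 3.1 | 3.10 | 3 | >3.0 | 3 |

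At b = 1.0 the two rules agreed at every multiple tried (1.6 to 5).

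**The case against.** The strongest reply is that little is lost.

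- Table 3 of Section 7.5.2 already counts rises by baseline multiple, up to Week 12 and over the entire period.
- Table 18 in Appendix 4 lists a creatinine shift table on those ranges by visit, including the four placebo-switch groups. Beyond the early period, the NCI-CTCAE shift table covers only the 100 mg and 150 mg groups.
- Actual values and changes from baseline are also summarised, and eGFR has its own row in Table 24.

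All of this stands, and it limits the point to one table.

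ULN-only grading may also have been intended. Creatinine carries the unit n/a, which footnote 1 reserves for criteria that depend strictly on the reference range. That is a fair reading, but the baseline limbs then contradict the footnote and should go.

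A reader might infer three stronger things that the documents do not support:

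- **That creatinine is under-graded against NCI-CTCAE v4.0.** The source text is not in the documents. Table 3 assigns no grades, so the shortfall can be stated only relative to its bands.
- **That large rises will go unreported.** Table 3 and its shift display report them.
- **That treatment suspension or adverse event grading is affected.** Investigators apply the protocol criterion and grade adverse events themselves; Table 24 feeds neither.

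**Conclusion.** The row is wrong as written. Its baseline limbs have no effect when baseline is at or below ULN, the Grade 3 limb never defines a separate grade, and grades overlap when baseline is above ULN. These results follow from the printed inequalities and need no assumption.

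The statement that the shift table misses large relative rises is made relative to Table 3 and rests on the mapping shown above. In the cases tabulated for baselines below ULN the gap is one or two grades, and it falls to nil as baseline reaches ULN. The documents give neither ULN nor the expected frequency of such rises, so the number of subjects affected cannot be estimated. Overlap needs a baseline above ULN. The renal exclusion (eGFR at or below 40 mL/min) does not by itself rule out a modestly raised baseline; the 2.5 × ULN case only illustrates the algebra.

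The effect is confined to the NCI-CTCAE creatinine shift table. No efficacy result, adverse event grade or suspension decision changes. It is a small correction, worth making because the printed row cannot be programmed unambiguously.

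**What to change.** Correct the creatinine row of Table 24 in one of two ways.

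1. **Keep baseline grading.** Set the Grade 2 baseline limb to "> 1.5 × Baseline to ≤ 3.0 × Baseline" and the Grade 3 baseline limb to above 3.0 × baseline, consistent with Table 3. Keep Grade 1 tied to values above ULN. Assign the highest grade met, and state that a baseline-limb grade overrides Grade 0 for a value still within normal limits. Amend the n/a entry, since the criteria would no longer depend on the reference range alone.
2. **Use ULN-only grading, if that was intended.** Delete the three baseline limbs. The row then agrees with footnote 1, and Table 3 carries the baseline-relative information.

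The cost is one table row and its program. Under the first option, somewhat more creatinine shifts would be reported at Grades 2 and 3. Under the second, nothing changes for subjects with a normal baseline, and subjects with a raised baseline get a unique grade. SAP Section 1 requires any change from the planned analyses to be justified in the clinical study report.

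### SAP Appendix 9 contradicts itself on uric acid: Table 24 grades every value above ULN up to 10 mg/dL as Grade 3, while a closing note says hyperuricemia is not in the table

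*SAP*

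**What the plan says.** SAP 7.5.2, under Laboratory Tests for NCI-CTC Toxicity Grading, says: "Laboratory test results for the select laboratory tests will be graded programmatically using the standardized NCI-CTC toxicity grading criteria". It adds: "Shift-from-baseline to worst value up to Week 12 or during entire period will be provided". For the criteria it refers the reader to Appendix 8.

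The grading table is in fact Table 24 in Appendix 9. Its Uric Acid row carries the term "Increase/ Hyperuricemia". Grade 0 is within normal limits, Grades 1 and 2 are empty, Grade 3 runs from above ULN to 10 mg/dL, and Grade 4 is above 10 mg/dL.

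Footnote 6 gives the reason for this layout: "Hyperuricemia Grade 3 is the same as Grade1 but has additional clinical criteria that cannot be assessed". It then records the decision: "it was decided to grade all criteria falling within >ULN – 10 mg/dL as grade 3".

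Three closing notes after the footnotes name items left out of the table. The one on hyperuricemia says that it "cannot be assessed accurately without knowing whether or not the subject was experiencing physiologic consequences, so it is not included in the table".

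**The concern.** The row and footnote 6 put hyperuricemia in the table, and the note says that it is not there. Both are current text in a one-version SAP, and a programmer cannot obey both. One would produce a graded shift table for uric acid, and another would produce none.

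The grade assigned is a second problem. Footnote 6 says that Grades 1 and 3 share a numeric range and differ only by clinical criteria that are unavailable. On that reasoning the laboratory value shows that a subject is at least Grade 1 and does not show Grade 3. The footnote nevertheless assigns Grade 3, which SAP 7.5.1.1 glosses as severe. Section 7.5.2 presents the criteria as the standardized ones, so a reader of the shift table may take Grade 3 at face value.

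At stake is the readability of one safety output for an analyte in the routine biochemistry panel (Protocol 5.4.4), which is drawn at every scheduled visit (Protocol Appendix 2).

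**Working it through.** The plan states no figure to reproduce, and the point is not one of sample size or error rate. The check applies each instruction as a decision rule and compares the results.

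**Step 1: do the row and the note concern the same item?** Yes. The row's NCI reference is page 116, and the note cites page 116 for hyperuricemia. The other two closing notes, on hemoglobinuria and troponin T, agree with the table, which has no row for either. Only the hyperuricemia note conflicts with it.

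**Step 2: apply each instruction.**

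| Uric acid result | Row and footnote 6 | Closing note |
|---|---|---|
| Within normal limits | Grade 0 | no grade |
| Above ULN to 10 mg/dL | Grade 3 | no grade |
| Above 10 mg/dL | Grade 4 | no grade |

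Under the row, Grades 1 and 2 can never occur.

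**Step 3: locate the jump.** The documents give no ULN for uric acid. Assume in turn 6.0, 7.0 and 8.0 mg/dL. Values of 6.1, 7.1 and 8.1 mg/dL, each 0.1 above the assumed limit, are all Grade 3, with or without symptoms. The result is the same for any ULN below 10 mg/dL by more than 0.1. A subject who enters with a value slightly above ULN is already Grade 3 at baseline, and a later rise that stays at or below 10 mg/dL shows no shift.

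**Step 4: compare with the other rows.** Uric acid is the only row in Table 24 whose lowest abnormal grade is 3. The nearest parallel is hypokalemia. Footnote 4 faces the same difficulty of a range shared by two grades and also takes the higher one, but there the result is Grade 2.

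**Step 5: trace the outputs.** The programmed grades feed the shift tables described in SAP 7.5.2, and SAP Appendix 4, Table 18, lists a shift table by CTCAE grade. Section 7.5.2 notes separately that adverse events are graded by the investigator, so the Grade 3 or higher TEAE summaries in SAP 7.5.1.1 and Appendix 3 do not use Table 24. The SAP plans no total of Grade 3 or worse laboratory results pooled over analytes.

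**Step 6: check the cross-reference.** SAP Appendix 8 lists adverse events of special interest. The reference in 7.5.2 therefore leads to the wrong appendix.

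**The case against.** The strongest reply is that footnote 6 is an open, pre-specified convention. Where two grades share a range and the data cannot separate them, the SAP takes the higher, and footnote 4 does the same for hypokalemia. Erring upward on safety is defensible, and moving to Grade 1 errs downward, because a symptomatic rise would then be shown as mild. Relabelling also moves no cut-off: the three bins stay the same, and so does every cell count. The size of uric acid rises remains visible elsewhere, because SAP 7.5.2 also gives raw values, changes from baseline, and shifts to highest and lowest value for all laboratory variables.

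Most of this stands. The upward convention alone is a choice, and the fix changes a label, not a count. Two things remain. The convention does not explain a note that excludes the same item from the same table. And a Grade 3 label on a value that the footnote itself cannot distinguish from Grade 1 tells the reader more than the data show. For hypokalemia the convention costs one step; here it places every mild rise in the severe category.

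A reader might infer more: that severe toxicity counts are inflated across the trial, or that a true severe signal is hidden. The documents do not support this. TEAE severity rests on investigator grades, and under Protocol 5.5.1 a laboratory abnormality becomes an adverse event only if it meets clinical criteria. Values above 10 mg/dL keep their own grade. A true Grade 3 cannot be identified from the laboratory value under either labelling.

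**Conclusion.** The contradiction is plain on the face of Appendix 9 and needs no assumption. Which version of the uric acid shift table is produced depends on which sentence the programmer follows. If the row governs, all values above ULN up to 10 mg/dL appear as Grade 3 without support for that grade.

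The reach is small. It covers one analyte in the laboratory toxicity-grade shift tables, under a rule that is the same in every arm. Adverse event severity tables, the Grade 4 category and the efficacy analyses are unaffected. It may be tempting to state what percentage of subjects would be mislabelled, but that needs a ULN and a distribution of uric acid in this population, and the documents give neither. This is an inexpensive correction worth making before programming; it does not threaten the trial's conclusions.

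**What to change.** Reconcile the row, footnote 6 and the closing note in Appendix 9. There are two consistent ways:

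- Delete the Uric Acid row and footnote 6, as the note implies. This loses the graded shift for uric acid; the ungraded laboratory summaries remain.
- Keep the row and delete the hyperuricemia note. Label the range above ULN to 10 mg/dL as Grade 1, or as Grade 1/3 not distinguishable, and keep values above 10 mg/dL as Grade 4. Footnote 6 should then say that Grade 3 cannot be determined from the laboratory value.

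The second way keeps the graded shift table. Its downside is that a symptomatic rise would not appear as Grade 3 there, although the investigator would still grade it if it is reported as an adverse event. If a lower or combined label is adopted, apply the same convention to hypokalemia in footnote 4.

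In the same edit, change the reference in SAP 7.5.2 from Appendix 8 to Appendix 9.

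The cost is a few lines of SAP text and no new data. If the SAP can no longer be revised, its Introduction provides for justifying the change in the clinical study report.
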